**Smith+Nephew**

## Clinical Protocol

### Pre-Registration Clinical Study

Study Number: CT1705POB

Version: 9.0, 04Aug2021

Page: 51 of 221

## 7.5 Informed Consent

Before conducting any study procedures or examinations, the purpose and nature of the study will be explained to the subject in their native language. The subject, or their legally authorized representative, will then **read, sign, and personally date** the IRB/IEC approved informed consent document(s) (see below for difficulties with reading and writing). Additionally, the individual who obtains consent from the subject will sign and date the informed consent document. A copy of the signed informed consent documentation will be provided to the subject, a copy will be placed in the subject's medical record, with the original filed in the ISF.

If the subject is unable to read, the informed consent document and associated study information may be read aloud to the subject in the presence of an impartial witness. If possible, the subject shall sign and personally date the Informed Consent Form (ICF). Where this is not possible, due to difficulties in writing, the subject shall provide verbal consent to participate in the study. The witness shall then personally sign and date the informed consent form, attesting that the information was accurately explained and that the informed consent was freely given.

All subjects will be given ample time (at least 24 hours) to consider participation following the explanation of the study/reading of the patient information sheet. If new information becomes available during the course of the study that can significantly affect a subject's future health and medical care, Smith + Nephew will ensure that information shall be provided to the subject(s) affected in written form and if relevant, all affected subjects shall be asked to confirm their continuing consent in writing.

**Smith+Nephew**

## **Clinical Protocol**

### **Pre-Registration Clinical Study**

Study Number: CT1705POB

Version: 9.0, 04Aug2021

Page: 52 of 221

## **7.6 Enrolment**

Enrolment in this study shall occur at the point the consent process has been completed and study number is allocated to the subject.

## **7.7 Lost to Follow-up**

A subject will be considered lost to follow-up if he/she does not appear for the 7 day, 14 day, or 30 day visit and study personnel are unable to contact the subject.

Some actively enrolled subjects will not return for follow-up exams on time. Study personnel must make a reasonable effort to contact the subject and document the following contact attempts prior to declaring a subject to be lost to follow-up: the subject has been contacted according to the site's policies, but no fewer than 2 documented phone contacts and 1 certified letter without response. Copies of all attempts to reach the subjects per regular mail or email and/or the attempts to contact the subject via other means should be documented and that documentation should be kept with the subject's source documents.

## **7.8 Withdrawal**

### **7.8.1 Withdrawal from Treatment**

Subjects may be withdrawn early from study treatment for the following reasons:

- Subject does not return following treatment (and pump is lost)

**Smith+Nephew**

## **Clinical Protocol**

### **Pre-Registration Clinical Study**

Study Number: CT1705POB

Version: 9.0, 04Aug2021

Page: 53 of 221

- Treatment is prematurely ended for any reason (i.e. due to removal of the system by the subject or the investigator, failure of the pump, dressing falls off, seal can no longer be established)
- Treatment is disrupted for longer than 24 hours (i.e. airtight seal was disrupted and was not re-established with a 24-hour time period).
- At the discretion of the Investigator due to:
  - A change in treatment is clinically warranted (to include further treatment following 7-day therapy).
  - An adverse event or device deficiency
  - Any other significant reason identified by the Investigator

### **7.8.2 Withdrawal from Study**

The Investigator **may** withdraw subjects from the study for many reasons, including but not limited to the following:

- subject lost to follow-up
- if the Investigator or the Sponsor stops the study for any reason and decides to withdraw subject(s) from the study
- any other significant reason identified by the Investigator

For each case, information will be obtained in the source document and the Case Report Form (CRF), detailing circumstances leading to the withdrawal.

Subjects who are withdrawn prior to the application of the study dressing will be replaced.

**Smith+Nephew**

## **Clinical Protocol**

### **Pre-Registration Clinical Study**

Study Number: CT1705POB

Version: 9.0, 04Aug2021

Page: 54 of 221

Subjects who are treated for bilateral knee surgery, and subjects who drop out, or are withdrawn, will not be re-entered into the study at a later date.

### **7.8.3 Subject's Withdrawal of Consent to Participate in Study**

Study participation is voluntary and subjects may withdraw at any point during the study without giving their reason for doing so. Where subjects withdraw consent, the Investigator should make a reasonable effort to ascertain the reason(s), while fully respecting the subject's privacy. The reason for withdrawal will be recorded in the CRF and in source documents.

### **7.8.4 Use of Data Following Withdrawal**

In cases where the subject withdraws consent, the data collected up to the point of withdrawal may be used but no additional data for that subject may be collected.

## **8 STUDY DESIGN**

### **8.1 Study Design**

This study is a prospective, multi-centre, non-randomised, non-blinded, single arm follow-up study to assess clinical performance and safety of [REDACTED] It is anticipated that up to 6 sites will participate within the UK.

The treatment phase will be 7 days post-surgery with a study follow-up period up to 30 days for assessment of complications. Seven days of therapy has been chosen as the length of time to assess device performance with use in real clinical conditions, since this is the length of time one system will operate and previous studies involving

**SmithNephew**

## **Clinical Protocol**

### **Pre-Registration Clinical Study**

Study Number: CT1705POB

Version: 9.0, 04Aug2021

Page: 55 of 221

---

incisions suggest that benefit is generally achieved over 7-10 days of NPWT therapy. The 30 day time period to assess safety and complications is given since previous literature suggests that most complications may occur during the first 30 days following surgery.

## Clinical Protocol

[figure not shown]
### Pre-Registration Clinical Study

Study Number: CT1705POB

Version: 9.0, 04Aug2021

Page: 56 of 221

**Smith+Nephew**

## **Clinical Protocol**

### **Pre-Registration Clinical Study**

Study Number: CT1705POB

Version: 9.0, 04Aug2021

Page: 57 of 221

## **8.2 Allocation and Blinding**

This study is non-randomised.

## **8.3 Data Management**

This study utilizes a validated, 21 CFR Part 11 compliant, electronic data capture system. Access to the electronic data capture system is controlled through Smith and Nephew procedures.

A Data Management Plan (DMP) is written according to Smith and Nephew procedures containing details of the data management process. The following is a brief description of the key points detailed in this plan.

### **8.3.1 Data Review and Quality Assurance**

Data will be transcribed from the data source to an electronic Case Report Form (eCRF). All data requested on the eCRFs are considered required. Data points not collected and/or recorded will be considered deviations unless otherwise specified.

Data collection is the responsibility of the clinical trial staff at the site under the supervision of the Principal Investigator. The Principal Investigator is responsible for ensuring the accuracy, completeness, legibility, and timeliness of the data reported. The Principal Investigator must provide his/her electronic signature on the appropriate eCRFs to be documented in compliance with local regulations. Changes to data previously submitted to the sponsor will require a new signature by the Investigator to acknowledge/approve the changes.

**SmithNephew**

## **Clinical Protocol**

### **Pre-Registration Clinical Study**

Study Number: CT1705POB

Version: 9.0, 04Aug2021

Page: 58 of 221

Visual and computer data review will be performed in line with Smith and Nephew procedures to identify possible data discrepancies. Manual and automatic queries will be created within the electronic data capture system, and will be issued by Smith and Nephew to the site for appropriate response. Site staff are responsible for resolving all queries in the electronic data capture system.

### **8.3.2 Retention Period**

All eCRFs will be archived once the study is completed and will be kept for a period of no less than five years after the later of the following dates: the date of which the study is terminated or completed; or the date that the records are no longer required supporting marketing applications.

## **8.4 Study Endpoints**

### **8.4.1 Primary Endpoint**

Functional clinical performance of [REDACTED] NPWT system over 7 days therapy to be assessed using a composite endpoint including the following components:

- Negative Pressure maintenance at nominal 80 mmHg [REDACTED]  
[REDACTED].
- Dressing wear time (7 days) as assessed through a combination of [REDACTED]  
[REDACTED] and CRF recorded data of any unplanned dressing change.
- Exudate management assessed by no occurrence of exudate leaks as assessed through clinical data on any leakage of exudate through a dressing or around

**Smith+Nephew**

## **Clinical Protocol**

### **Pre-Registration Clinical Study**

Study Number: CT1705POB

Version: 9.0, 04Aug2021

Page: 59 of 221

the borders observed during the dressing wearing period resulting or not, in an unplanned dressing change.

### **8.4.2 Secondary Endpoints**

Clinical performance and safety of the [REDACTED] NPWT system over a 30 day follow-up period to include:

- Incidence of Surgical Site Infection (SSI) – Superficial, deep, organ [CDC criteria] within 30 days of surgery
- Incidence of Surgical site Complications (SSC) [as applicable: dehiscence (superficial/deep, partial/total), seroma, necrosis, hematoma, suture abscess] within 30 days of surgery
- Condition of peri-wound skin and skin under the pump [REDACTED] assessed through visual inspection at 7, 14 and 30 days.
- Wound and Skin VAS score assessment at 7, 14 and 30 days
- *Phase 1 only:* Comparison of Wound and Skin VAS scores at days 7, 14 and 30 as assessed by the treating clinicians versus scores provided by the independent assessor.
- *Phase 1 only:* Range of motion assessment (for knee subjects only) at pre-operative, post-operative day 1, 7, 14 and 30 days
- Level of pain during wear of the [REDACTED] system, and at dressing removal assessed by VAS scale following 7-day therapy

**Smith+Nephew**

## **Clinical Protocol**

### **Pre-Registration Clinical Study**

Study Number: CT1705POB

Version: 9.0, 04Aug2021

Page: 60 of 221

#### **8.4.3 Exploratory Endpoints**

- Clinician acceptability of [REDACTED] system at discontinuation of therapy
- Subject acceptability of [REDACTED] system at discontinuation of therapy
- Ease of application & removal
- Subject comfort during wear.
- A descriptive analysis for clinician's and subject's experience of the device and perception of the device in general will be included in the analysis.

#### **8.4.4 Safety Endpoints**

Safety, assessed through the incidence and severity of Adverse Events and Device Deficiencies

### **8.5 Methods Used to Minimize Bias and Maximize Validity**

#### **8.5.1 Reduction of bias towards acceptability of IP system when compared with other manufacturers/models**

Smith & Nephew will ensure that reduction of bias towards acceptability of the [REDACTED] [REDACTED] system against any others marketed, by being fully transparent with the aim of the study prior to commencing and through publishing the result of the primary endpoint following reporting on [www.clinicaltrials.gov](http://www.clinicaltrials.gov) and any other applicable trial registries.

**Smith+Nephew**

## **Clinical Protocol**

### **Pre-Registration Clinical Study**

Study Number: CT1705POB

Version: 9.0, 04Aug2021

Page: 61 of 221

#### **8.5.2 Minimisation of bias due to low study numbers**

The statistical techniques for the study have attempted to account for bias brought about by low subject numbers. Subject attrition has been accounted for within the sample size calculation. This sample size was based on a previous PICO study data using similar data loggers.

#### **8.5.3 Attempt to retain ecological validity**

Phase 1 of the study included a single indication in two different surgical specialties and a range of contoured areas of the body where it may be difficult to obtain an effective negative pressure seal and where there may be a range of motion throughout therapy (i.e. knee). The inclusion/exclusion criteria are also not too restrictive with regard to subject demographic. This should mean that the results will be representative of a real clinical setting in hospital or at home, and for the proposed indication in the two specialties.

#### **8.5.4 Attempt to reduce ascertainment bias in data collection**

Subject and clinician will also be requested to verify any answer they give with some rationale for their answer where possible.

**Clinical Protocol****Pre-Registration Clinical Study**

Study Number: CT1705POB

Version: 9.0, 04Aug2021

Page: 62 of 221

**9 STUDY PROCEDURES****9.1 Visits and Examinations****9.1.1 Summary****Figure 3 Study Procedures by Visit**

Schedule of events	Pre-Operative Data (Up to 6 weeks pre-surgery )	Operative Data	Baseline Post-Operative Data (within 24 ± 3 hours)	Dressing Inspection 4 ± 1 day	End of Therapy Assessment 7 days	Day 14 FU (14 (± 3) days)	Exit Visit Day 30 FU (30 (± 3) days)	Unscheduled Visit or Early Exit
Informed Consent	x							
Inclusion/Exclusion	x	x						
Demographics/Vital Signs/Medical History/History of Substance Use	x							
Concomitant Medication Check	x	x	x	x	x	x	x	x
Subject Comfort Level and VAS Pain Score				x	x			
Acceptability of NPWT system to Subject					x			
Assessment of NPWT application by Clinician		x						
Acceptability of NPWT system to Clinician					x			

**Clinical Protocol**

Study Number: CT1705POB

**Pre-Registration Clinical Study**

Version: 9.0, 04Aug2021

Page: 63 of 221

Schedule of events	Pre-Operative Data (Up to 6 weeks pre-surgery )	Operative Data	Baseline Post-Operative Data (within 24 ± 3 hours)	Dressing Inspection 4 ± 1 day	End of Therapy Assessment 7 days	Day 14 FU (14 (± 3) days)	Exit Visit Day 30 FU (30 (± 3) days)	Unscheduled Visit or Early Exit
Instructions/ Education For Subject &/Or Care Givers			x					
Operative Data Collection & Dressing application		x						
Range of Motion Assessment (for knee subjects in phase 1 only)	x		x*		x**	x	x	
Photographic & Incision Assessment		x			x	x	x	x
Treatment Data Collection & Dressing removal					x			
Incision complications assessment		x			x	x	x	x
Adverse Event Assessment		x	x	x	x	x	x	x
Device Deficiency Assessment		x	x	x	x			
End of Study/Exit							x	x

\* post dressing application

\*\* Pre and post dressing removal

**9.1.2 Screening/Preoperative Visit (may be up to 6 weeks prior to operative visit)**

NOTE: Any subject who signs an informed consent but fails to meet the required entry criteria is considered to be a Screen Failure. Information must be captured in the appropriate CRFs up to the point of screen failure with the reason for screen failure specified (section 7.4).

1. Obtain written informed consent from the subject as detailed in Section 7.5

----- **Do not proceed until consent has been obtained** -----

2. Obtain demographic information and medical history (for current or chronic conditions as per the eCRF categories), including information on all concomitant medications/therapies.
3. Screen the subject for protocol inclusion/exclusion criteria.
4. Obtain range of motion measurements (for knee subjects only in Phase 1)
5. Subjects will be instructed to return to the treatment facility for the Operation Visit (within 6 weeks of consent).

**9.1.3 Baseline Operative Visit (Within 6 weeks of screening)**

NOTE: Any subject who has signed an informed consent but at this visit no longer meets the required eligibility criteria prior to the study dressing application is considered to be a Screen Failure. Information must be captured in the appropriate CRFs up to the point of screen failure with the reason for screen failure specified (section 7.4).

1. Query subject regarding any changes in general health and the use of concomitant medications (if screening and surgery are not on the same date).
2. Commence operation and collect surgery data [e.g. Type of surgery (closed surgical incision, (type of abdominal surgery, type of knee surgery, incision length, anatomical location and method of closure),
3. Collect surgery risk factors (elective/emergency surgery, laparoscopic (y/n), incision length, use of prophylactic antibiotics, type (single/double/triple

## CONFIDENTIAL AND PROPRIETARY

This document contains information that is confidential and proprietary to Smith & Nephew PLC and Smith & Nephew, Inc. and is intended for use only by Smith & Nephew and its manufacturer. It shall not be reproduced or copied in whole or in part, nor shall the contents be disclosed by any means without prior written permission from Smith & Nephew, nor shall anyone make any use of it that is contrary to the expressed or implied wishes of Smith & Nephew.

\_\_\_\_\_ - \_\_\_\_\_ - \_\_\_\_\_

**Clinical Protocol - Device****Pre-Registration Clinical  
Study**

Study Number:  
CT1705POB  
Version: 9.0 04Aug2021  
Page: 65 of 221

agent) and when administered (prior to start of surgery/after surgery began), shaving of incision (yes/no/not needed), use of a wound protector (yes/no), surgical bioburden level(clean/clean-contaminated/contaminated/dirty), intraoperative warming (yes/no))

4. Confirm eligibility following surgery details. NOTE: Subjects that no longer meet the eligibility criteria following surgery will be deemed a screen failure; operative information must be captured in the appropriate CRF with the reason for screen failure specified. These subjects will be replaced.
5. Photograph incision using the camera ( [REDACTED] ) provided by the Sponsor.
6. Assess the incision characteristics for likelihood of SSC (oedema, seroma, haematoma, skin necrosis).
7. Assess the surrounding skin including the area under the pump (e.g., healthy, fragile, inflamed, erythema, bruising, eczematous, dry/flaky, macerated).
8. Dispense study product. Record pump lot number, size of dressing used [REDACTED] and any ancillary products applied (SECURA No-Sting Skin prep, RENASYS Adhesive Gel Patch). Record also ancillaries in the vicinity (e.g. drains, stomas, lines, dressings).
9. Assess ease of application, ease of establishing seal/negative pressure delivery, satisfaction of applying IP.
10. Take photograph of dressing in place. Take a photograph of the carton label to aid accountability checks (the label will contain the batch number).
11. If any adverse device effects or device deficiencies are observed or reported, they must be recorded as instructed in Section 12 - Adverse events and device deficiencies.
12. If there were failed attempts at applying the study product. Please record the device details and disposition of the device.

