#### **CONFIDENTIAL AND PROPRIETARY**

This document contains information that is confidential and proprietary to Smith & Nephew PLC and Smith & Nephew, Inc. and is intended for use only by Smith & Nephew and its manufacturer. It shall not be reproduced or copied in whole or in part, nor shall the contents be disclosed by any means without prior written permission from Smith & Nephew, nor shall anyone make any use of it that is contrary to the expressed or implied wishes of Smith & Nephew.

[REDACTED] - [REDACTED] - [REDACTED]

**Clinical Protocol - Device****Pre-Registration Clinical  
Study**

Study Number:

CT1705POB

Version: 9.0 04Aug2021

Page: 67 of 221

more, clinician recommends a change in treatment, at the discretion of the Investigator, adverse event, subjects own request, lost to follow-up, other).

3. Record the use of concomitant medications.
4. Record reason if dressing is no longer in place (e.g. pain/discomfort from the dressing, subject removed, subject's request, adverse event, no vacuum, pump turned off, other).
5. Record if therapy has been interrupted since the previous assessment and how long.
6. Take photograph of dressing in place
7. Obtain range of motion measurements (for knee subjects only in Phase 1)
8. Assess subject satisfaction (overall performance of dressing, comfort, noise level, discreteness, portability, interference with daily living – showering, sleeping, socialising, working).
9. Remove NPWT system as per procedure (section 9.2.4) for [REDACTED]. Record the unique device identifier [REDACTED] [REDACTED].
10. Assess ease of removal.
11. Record pain score (VAS) and subject comfort since last assessment and pain score on dressing removal.
12. A suitably qualified individual (as described in section 9.2.1) to complete CDC incision assessment and incision closure.
13. A suitably qualified individual (as described in section 9.2.1) to complete assessment of incision complications. If any complications have occurred, details of this and additional procedures to be collected (per section 9.1.9).
14. Assess the surrounding skin (e.g., healthy, fragile, inflamed, erythema, bruising, eczematous, dry/flaky, macerated)
15. Assess the skin area under the pump (e.g., healthy, fragile, inflamed, erythema, bruising, eczematous, dry/flaky, macerated)
16. Obtain range of motion measurements (for knee subjects only in Phase 1)

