### **9.2.4 Photographs and Surgical Site Assessment**

Images of the subject's postsurgical incision (and wound zone) will be captured prior to initial dressing application, at 7 days post operatively (or when dressing is removed), at 14 days and at 30 days postoperatively (or early exit visit) using a digital camera supplied by S&N.

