## 10.3 Baseline Data

The subjects will be described and summarised using the baseline demographic and medical variables which include but are not limited to age, gender, ethnicity, medical and medication history, diagnostic factors. Summary statistics will be given according to the nature of the variable, continuous or categorical. For categorical variables, the number of observations,

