#### **CONFIDENTIAL AND PROPRIETARY**

This document contains information that is confidential and proprietary to Smith & Nephew PLC and Smith & Nephew, Inc. and is intended for use only by Smith & Nephew and its manufacturer. It shall not be reproduced or copied in whole or in part, nor shall the contents be disclosed by any means without prior written permission from Smith & Nephew, nor shall anyone make any use of it that is contrary to the expressed or implied wishes of Smith & Nephew.

[REDACTED] - [REDACTED] - [REDACTED]

Smith+Nephew

**Clinical Protocol - Device****Pre-Registration Clinical  
Study**

Study Number:  
CT1705POB  
Version: 9.0 04Aug2021  
Page: 86 of 221

- Incidence of Surgical site Complications (SSC) [as applicable: dehiscence (superficial/deep, partial/total), seroma, necrosis, hematoma, suture abscess] within 30 days of surgery
- Wound and Skin VAS score assessment at 7, 14 and 30 days
- Condition of peri-wound skin and skin under the pump [REDACTED] assessed through visual inspection at 7, 14 and 30 days.
- Level of pain during wear of the [REDACTED] system, and at dressing removal assessed by VAS scale following 7-day therapy
- Phase 1 only: Comparison of Wound and Skin VAS scores at days 7, 14 and 30 as assessed by the treating clinicians versus scores provided by the independent assessor.
- Phase 1 only: Range of motion assessment (ROM) for the knee at pre-operative visit, post-operative visit, 7, 14 and 30 days.
- Level of pain during dressing removal (VAS scale) - pain intensity as none, mild, moderate, or severe.

For incidence of SSI and incidence of SSC binary variables indicating presence of/absence of will be defined and the frequencies together with percentages reported/identified outcomes will be reported separately for each specialty. A logistic model will be used to evaluate the adjusted and the un-adjusted models for the secondary variables, the incidence of surgical site infections, and incidence of surgical complications separately for each specialty. The variables considered important and to be included in the final model are Age, Diabetic status and the presence of any other co-morbidity as a binary variable. All other baseline and medical factors collected at baseline will be evaluated for importance in adjusted models and only those statistically significant in an un-adjusted model will be considered in the final model.

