## CONFIDENTIAL AND PROPRIETARY

This document contains information that is confidential and proprietary to Smith & Nephew PLC and Smith & Nephew, Inc. and is intended for use only by Smith & Nephew and its manufacturer. It shall not be reproduced or copied in whole or in part, nor shall the contents be disclosed by any means without prior written permission from Smith & Nephew, nor shall anyone make any use of it that is contrary to the expressed or implied wishes of Smith & Nephew.

[REDACTED] - [REDACTED] - [REDACTED]

**Clinical Protocol - Device****Pre-Registration Clinical  
Study**

Study Number:  
CT1705POB  
Version:9.0 04Aug2021  
Page: 87 of 221

between assessors where appropriate. In each case analyses will be presented separately for each specialty.

Summary statistics for all other secondary variables will be given, for each specialty separately, according to the nature of the variable, continuous or categorical. For categorical variables, the number of observations, mean, standard deviation, median, minimum, and maximum will be presented, while for categorical variables the number of observations, frequency, and percentages will be reported. 95% confidence intervals will be reported where appropriate.

As range of motion is collected for subjects in the knee surgery group only there will be no summary of ROM in the s-FAS and s-PP analysis.

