## CONFIDENTIAL AND PROPRIETARY

This document contains information that is confidential and proprietary to Smith & Nephew PLC and Smith & Nephew, Inc. and is intended for use only by Smith & Nephew and its manufacturer. It shall not be reproduced or copied in whole or in part, nor shall the contents be disclosed by any means without prior written permission from Smith & Nephew, nor shall anyone make any use of it that is contrary to the expressed or implied wishes of Smith & Nephew.

[REDACTED] - [REDACTED] - [REDACTED]

**Clinical Protocol - Device****Pre-Registration Clinical  
Study**

Study Number:  
CT1705POB  
Version: 9.0 04Aug2021  
Page: 125 of 221

	Sting Skin prep, RENASYS Adhesive Gel Patch).	Adhesive Gel Patch). Include also ancillaries in the vicinity (e.g. drains, stomas, lines, dressings).
9.1.3 Baseline Operative Visit	10. Take photograph of dressing in place.	10. Take photograph of dressing in place. Take a photograph of the carton label to aid accountability checks (the label will contain the batch number).
9.1.4 Baseline Post-Operative visit	3. Obtain range of motion measurements (knee subjects only)	3. Obtain range of motion measurements (for knee subjects only in Phase 1)
9.1.6 End of Therapy Assessment	7. Obtain range of motion measurements (knee subjects only)	7. Obtain range of motion measurements (for knee subjects only in Phase 1)
9.1.6 End of Therapy Assessment	14. Assess the surrounding skin including the area under the pump (e.g., healthy, fragile, inflamed, erythema, bruising, eczematous, dry/flaky, macerated)	13. Assess the surrounding skin (e.g., healthy, fragile, inflamed, erythema, bruising, eczematous, dry/flaky, macerated)
9.1.6 End of Therapy Assessment	15. Obtain range of motion measurements (knee subjects only)	14. Assess the skin area under the pump (e.g., healthy, fragile, inflamed, erythema, bruising, eczematous, dry/flaky, macerated)
9.1.7 Day 14	4. Assess the surrounding skin including the area under the pump (e.g., healthy, fragile, inflamed, erythema, bruising, eczematous, dry/flaky, macerated)	4. Assess the surrounding skin (e.g., healthy, fragile, inflamed, erythema, bruising, eczematous, dry/flaky, macerated)
		5. Assess the skin area under the pump (e.g., healthy, fragile, inflamed, erythema, bruising, eczematous, dry/flaky, macerated)

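### Skin under the pump is scored with the surrounding skin at baseline but separately at Days 7, 14 and 30, and the planned summary does not separate new from pre-existing findings

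*Combined protocol and SAP*

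**What the plan says.** At the operative visit the protocol has a single skin item, placed before the study product is dispensed (section 9.1.3 step 7): "Assess the surrounding skin including the area under the pump (e.g., healthy, fragile, inflamed, erythema, bruising, eczematous, dry/flaky, macerated".

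At the end-of-therapy visit the surrounding skin is step 14 of section 9.1.6, and step 15 is a separate item: "Assess the skin area under the pump (e.g., healthy, fragile, inflamed, erythema, bruising, eczematous, dry/flaky, macerated". Sections 9.1.7 (Day 14) and 9.1.8 (Day 30) have the same pair as steps 4 and 5.

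Section 10.4.2 lists the secondary endpoint as "Condition of peri-wound skin and skin under the pump [REDACTED] assessed through visual inspection at 7, 14 and 30 days". It names no method specific to this endpoint, so the endpoint falls under the general rule: "Summary statistics for all other secondary variables will be given, for each specialty separately, according to the nature of the variable, continuous or categorical". Section 10.3 describes subjects by "baseline demographic and medical variables which include but are not limited to age, gender, ethnicity, medical and medication history, diagnostic factors". Baseline skin is not named there, although the list is open-ended.

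Section 9.2.4 adds a photographic record: "Images of the subject's postsurgical incision (and wound zone) will be captured prior to initial dressing application".

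The Amendment 8 log (section 22.2.4) shows that under v7.0 the Day 7 item was also combined: "14. Assess the surrounding skin including the area under the pump". The Day 14 and Day 30 items were combined in the same way.

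**The concern.** The condition of the skin under the pump is a named secondary objective (section 5.2) and endpoint (section 8.4.2). It is one of the places where this study looks for local harm from the device. The study has a single arm, so each subject's own skin before application is the only within-study reference for a device effect.

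Several of the listed categories can be present before the device is applied. Bruising or erythema may be there at the end of surgery. Fragile skin is compatible with enrolment: exclusion 2 removes such subjects only if they need the barrier wipes and are hypersensitive to them, and section 6.1.3 supplies the wipes for fragile skin. An entry of fragile at Day 7 may simply repeat the baseline.

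If the table counts every listed finding at Day 7 without regard to baseline, the reader cannot tell how much of the count arose during wear. The error could run either way. Pre-existing findings could be read as device effects, or a real effect could be dismissed as probably pre-existing.

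**Working it through.** No sample-size or power figure is involved. The check sets the visit procedures beside the analysis text.

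**Step 1: what is scored at each visit (v9.0)**

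| Visit | Section | Surrounding skin | Skin under the pump |
|---|---|---|---|
| Operative, before application | 9.1.3 | step 7, combined | step 7, combined |
| Day 7 | 9.1.6 | step 14 | step 15 |
| Day 14 | 9.1.7 | step 4 | step 5 |
| Day 30 | 9.1.8 | step 4 | step 5 |

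**Step 2: where the mismatch came from.** The Amendment 8 log splits the item at Days 7, 14 and 30. Its entries for section 9.1.3 change only steps 8 and 10, and step 7 is left alone. No reason is given for treating baseline differently, which suggests an oversight.

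**Step 3: what the scored items can show when there is a later finding under the pump**

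- *Combined baseline healthy.* The finding is new, and the scored data show it.
- *Combined baseline abnormal, later finding in a different category.* The finding can be called new, provided the form records every category present.
- *Combined baseline abnormal, later finding in the same category.* The score does not say whether the baseline finding lay under the pump or elsewhere, so the later finding cannot be classified from the item.

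**Step 4: what the planned summary shows.** Section 10.4.2 gives descriptive statistics at Days 7, 14 and 30. It specifies no shift table, no change from baseline and no definition of a new finding. The models with baseline covariates cover composite clinical success, SSI and SSC, not skin. As written, the table does not separate new from pre-existing findings even in the first case, where the data would allow it.

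**Step 5: pooling across protocol versions.** Section 11.2 gives 66 abdominal subjects: 22 under v7.0 and 44 in the second phase. The v7.0 subjects had the combined site-scored item at every visit. They make up 22/66 = 33% of the pooled abdominal set. A pooled under-pump row would therefore put two differently defined items together unless the combined one is labelled.

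**The case against.** The strongest reply is that the trial as a whole holds more information than the skin tally.

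- Baseline does cover the pump area, and a healthy entry settles the matter for that subject.
- The wound zone is photographed before application, framed to take in the dressing area (section 9.2.4).
- The skin check looks for adverse events under the dressing (section 9.2.2), and each adverse event is rated for its relationship to the device (section 12.3).
- Exclusions 4 and 9 remove subjects whose skin features would interfere with assessments or who have infected skin lesions.
- Section 10 is a summary, and a fuller SAP is to follow.

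Most of this stands, and it limits the point. A reader might infer that new device-caused changes cannot be told from earlier ones at all. The documents do not support that, for the first three reasons above. Nor do they show that baseline skin will never be used in the analysis; section 10 is silent and does not rule it out.

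A reader might also infer that the 22 v7.0 subjects have no under-pump result. That does not follow either. Under v7.0 section 9.2.1, as reproduced in the Amendment 8 log, an independent assessor reviewed photographs with particular attention to the skin under the pump. What those subjects lack, on the protocol text, is a separate site-scored item. The eCRF is not available and may differ.

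A further tempting inference is that pooling hides the separately scored result. Sections 10.2 and 10.4 already plan s-FAS and s-PP analyses of post-interim subjects. Section 10.4.2 confirms that these reach the secondary endpoints, because it has to exempt range of motion.

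Three things survive. No stated analysis uses the photographs to score baseline skin under the pump, and Amendment 8 removed the independent photographic read. Causality ratings inform individual events but do not change what the endpoint table counts. A later SAP can add a shift table, but it cannot restore to the scored item a location that was never entered.

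**Conclusion.** The point holds in a limited form. The planned skin summary mixes new and pre-existing findings. When the combined baseline is abnormal and the same category recurs under the pump, the scored item cannot show whether the finding was already there.

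The number of subjects affected cannot be calculated from the documents, which give no rate of abnormal skin at the end of surgery. A reader might assume a rate to get a count. An assumed 5% to 30% of 66 would be 3.3 to 19.8 subjects. No document supports that range, and using it would also require every baseline finding to persist to Day 7, to appear under the pump and to remain unresolved by the photographs. It should not be read as an estimate.

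The endpoint is secondary and descriptive, with no test or threshold attached. The primary endpoint and sample size are unaffected. The change is still worth making, because it gives a single-arm safety and performance endpoint its only within-subject reference at almost no cost. The conclusion assumes that the eCRF follows the visit procedures as written and that no fuller SAP already specifies a comparison with baseline.

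**What to change.** 1. Split section 9.1.3 step 7 into the same two items used in sections 9.1.6 to 9.1.8: surrounding skin, and skin where the pump will sit.
2. In section 10.4.2, or in the SAP before database lock, report peri-wound skin and under-pump skin each as a shift from the operative baseline at Days 7, 14 and 30, with findings classed as new or worsened versus already present. The listed categories carry no grade, so worsened needs a definition.
3. Use the planned s-FAS and s-PP for the separately scored under-pump result. In any pooled table, label the site-scored item from the 22 v7.0 abdominal subjects as combined.

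The cost is one extra eCRF field, at an assessment already being made, and one table. The limitation is that a site-specific shift will exist only for subjects enrolled after the split. Second-phase subjects enrolled before it will have separate items at Days 7, 14 and 30 but only a combined baseline, and the table should say so.
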